4.2 Risk/Benefit assessment

Traditionally, management recommendations for rheumatic diseases (and reimbursement criteria in Belgium) follow a step-up strategy, starting with non-steroidal anti-inflammatory drugs (NSAIDs) and/or conventional synthetic disease modifying anti-rheumatic drugs (csDMARDs) as first line treatment options. Biologic DMARDs (bDMARDs), including TNFi, are recommended as second line treatment in patients with refractory disease. While treatment in these cases is still very effective, there is a significant percentage of patients that does not achieve a relevant improvement and in most cases prolonged (life-long) treatment will be necessary.

We hypothesized that by first line use of bDMARDs in an early disease stage, the clinical response would not only be better, but that early induction of remission could also permit the temporary use of a bDMARD (allowing the patient to reach a status of “drug-free remission”). We have tested this hypothesis in a proof of concept study, the CRESPA trial (Clinical Remission in very Early SPondyloArthritis), in which patients with peripheral SpA and less than 3 months of symptom duration, were randomized to TNF inhibition (TNFi) with golimumab versus placebo (Carron P, et al. *Ann Rheum Dis*. 2017; Carron P, et al. *Arthritis Rheumatol*. 2018). In this pilot trial we were able to demonstrate that 82% of all included patients achieved complete resolution of symptoms (arthritis, enthesitis, dactylitis), after which treatment with golimumab was discontinued. Intriguingly, over 50% of patients were staying in drug-free remission (with currently a follow-up of >2 years). Hence, the CRESPA trial pointed for the first time to the possibility of inducing drug-free remission in a significant proportion of patients suffering from a disease that had been previously considered to require lifelong medication.

There were some challenges and limitations with regard to the CRESPA trial:

- The main challenge was the fact that patients could not have signs or symptoms of arthritis/enthesitis/dactylitis for >3 months. This required an extensive referral network with fast-track consultations to check eligibility for trial inclusion. As a consequence, the CRESPA trial consisted of a very specific pSpA population with extremely short symptom duration. We do not know if the results (high rates of clinical remission with TNFi-treatment; significant percentage of patients in drug-

free remission after TNFi-withdrawal) can be extrapolated to a pSpA population with longer symptom duration.

- The main limitation of the CRESPA trial was the fact that the control group consisted of placebo. This was done in order to be able to estimate the rate of spontaneous clinical remission in this population (which was remarkably low), but one could argue that in daily practice such patients would have been treated with csDMARDs.

The current SPARTACUS trial will address both issues:

- Peripheral SpA patients with a symptom duration up to 1 year at screening will be eligible for inclusion. This will allow us to evaluate if there is a specific window of opportunity timeframe when the disease is more susceptible to effective treatment.
- In SPARTACUS, we will not compare the “TNFi-Induction” group with placebo, but with a more daily practice “csDMARD-Step-up” treatment strategy.

The obvious advantages for the patients participating in this trial will be the early access to bDMARD therapy (at a stage where Belgian reimbursement would not allow this effective therapy) and the fact that (compared to the CRESPA trial) there is no risk of placebo-treatment. While it could be considered that TNFi treatment can be associated with side effects, these drugs are currently indicated and reimbursed for multiple diseases in the SpA-concept, albeit in the more longstanding phases of the disease when there is already definitive structural damage.

4.3 Patient participation in trial design

Not applicable

5 Objective(s) of the study

5.1 Main objectives

The SPARTACUS study will explore the therapeutic efficacy of 2 different treatment strategies for patients suffering from peripheral Spondyloarthritis (pSpA), classified according to the “Assessment in SpondyloArthritis international Society” (ASAS) classification criteria (1) (see Addendum 1); it will be set up as a 48-week, prospective, randomized, active-comparator controlled, double-blind, double-dummy, clinical trial with a two-fold clinical objective:

- To compare a standard step-up approach using conventional synthetic Disease-Modifying Anti-Rheumatic Drugs (csDMARDs), such as methotrexate and/or sulphasalazine (the “csDMARD Step-Up”-strategy), with an early remission-induction treatment strategy that immediately introduces biological DMARDs (bDMARDs) as the first step in the treatment algorithm; in this group the Tumor Necrosis Factor inhibitor (TNFi) golimumab will be utilised (the “TNFi Induction”-strategy).

The double-blind phase of the study will compare the 2 treatment strategies with regard to the proportion of patients that achieve a status of (sustained) clinical remission.

In patients that reach sustained clinical remission, all study treatments (both in the “csDMARD Step-up”-group and the “TNFi Induction”-group) will be stopped, and long-term, clinical follow-up of these patients will allow to explore the possibility of “drug-free remission”; also with regard to this objective, the difference in symptom duration will be evaluated.

5.2 Secondary objectives

To try to define the window of opportunity within which temporary treatment with bDMARDs might be more effective, by analysing patients according to symptom duration, either as a continuous variable, or by comparing patients with shorter symptom duration (<3 months) versus those with more longstanding disease (between 3-12 months of symptom duration).

SPARTACUS trial is part of a bigger SPARTACUS project of the VIB Grand Challenges Program and will have several achievable goals:

1. To show superiority of early treatment of pSpA patients with bDMARDs as compared to standard of care.

In current practice, TNFi, the predominant bDMARDs in SpA, are only reimbursed in a restricted number of indications: they can be prescribed for axial spondyloarthritis (axSpA) and for the specific pSpA-entity, psoriatic arthritis (PsA); however, even in PsA, they are only reimbursed for longstanding, erosive disease, when patients have already failed (multiple) csDMARD(s). In patients with pSpA without psoriasis, rheumatologists can only prescribe csDMARDs, because TNFi are still off-label despite the overall good efficacy observed in several proof-of-concept studies, incl. one phase 3 trial (Ability-2) (2). For this subgroup of patients, the unmet need is therefore still unacceptably high. Moreover, the patients included in Ability-2 reflected the current step-up treatment paradigm: patients already had longstanding disease (symptom duration of approx. 7 years) and had used (and failed) conventional treatment options before trial entry (99% prior use of Non-Steroidal Anti-Inflammatory Drugs (NSAIDs), 69% prior csDMARD use). In this population, a statistically significant difference between adalimumab and placebo was observed, but clinical remission rates remained somehow disappointing with only 33% of patients reaching the predefined remission outcome after 3 years of continuous adalimumab use (3).

Until recently, no data were available regarding the treatment of early pSpA with bDMARDs. To address this knowledge gap, we designed a proof-of concept study to explore the therapeutic potential of TNFi in patients with pSpA with very short symptom duration, the CRESPA-trial (4). In this study, all patients had a symptom duration of less than 12 weeks: they were randomized to receive either immediate TNFi therapy (golimumab) or placebo. In summary, the results of this trial demonstrated that after 24 weeks of treatment, complete clinical remission could be achieved in 75% of golimumab-treated patients versus only 20% in patients treated with placebo (thus refuting the perception that a large majority of pSpA patients would go in spontaneous clinical remission). Due to the placebo-controlled design, the CRESPA trial did not provide any data on the percentage of patients that would have achieved clinical remission while on standard-of-care “csDMARD Step-up” treatment. The design of the SPARTACUS head-to-head trial will allow us to evaluate superiority of the new approach to current practice.

2. To delineate the window of opportunity for intensive treatment of pSpA: a transient time frame in which a disease is more susceptible to treatment.

In the proof-of-concept CRESPA trial, all included patients had a symptom duration of less than 12 weeks. In these patients very high clinical remission rates were observed when patients were immediately treated with a TNFi. Interestingly, when the bDMARD treatment was interrupted after reaching sustained remission, 53% of patients remained in drug-free remission at long-term follow-up (5), providing preliminary evidence for the “window of opportunity” hypothesis: by effectively tackling pSpA (with bDMARDs) in a very early phase of the disease, drug-free remission might be an achievable goal in a significant number of patients. However, the CRESPA-trial does not allow to generalize the findings to pSpA patients with longer symptom duration. Moreover, the above-mentioned extension of the Ability-2 study would suggest that patients with a symptom duration of multiple years would have lower remission rates and would need chronic, life-long bDMARD treatment. The SPARTACUS trial will still focus on early treatment of pSpA (symptom duration <12 months), and will analyse the effect of symptom duration on reaching the different outcomes. The goal is to demonstrate that drug-free remission is a feasible outcome when an early intensive treatment strategy is adopted and to delineate the window of opportunity (in terms of symptom duration) in which such a remission-induction strategy is successful, leading to significant health economic benefits (goals 4 and 5).

3. To unravel new biomarkers of therapy response using cutting-edge single cell technology.

In the CRESPA trial, we observed that despite the fact that 53% of patients were able to achieve drug-free remission, a significant proportion nevertheless relapsed. In this small proof-of-concept study, we were not able to detect significant predictors or remission or relapse. Also, 18% of patients did not achieve sustained clinical remission, but nevertheless experienced a significant improvement of signs and symptoms; in these patients long-term treatment was necessary. These results indicate that clinical response to TNFi is heterogeneous and underscores the need for biomarkers that can identify at baseline different pathogenic subsets that are associated with the (lack of) response to a TNFi. The recent introduction of new procedures such as ultrasound-guided synovial biopsy sampling in our early arthritis clinic has permitted to access synovial samples of virtually all peripheral joints (incl. wrists and small finger joints). By using innovative and unbiased tools recently developed in the area of single-cell analyses (RNA-sequencing and epigenetic profiling) by VIB and KU Leuven, we will obtain profound insights into the cellular heterogeneity of these unique patient samples.

4. To determine health-economic and societal impact of early, intensive bDMARD treatment of patients with recent-onset pSpA (compared to the currently reimbursed csDMARD Step-up strategy).

A unique feature of SPARTACUS is that clinical trial and biomarker discovery will be coupled to calculation of the health-economic benefits of such an approach. We aim to determine from a healthcare and a societal perspective, the 2 years’ cost-utility, as well as a model-based lifelong incremental cost-utility of the innovative strategy compared to usual care. Uncertainty analyses will be performed and budget impact for the Belgian healthcare and social security (work disability) system will be calculated by Maastricht University. Consistent with the increased call for transparency in health economic modelling, we aim to make our model available as a semi-open source model.

5. To increase awareness among referring physicians (general practitioners, other specialties that may evaluate patients with early SpA) and patient-advocacy groups about the value of early recognition and treatment in rheumatology.

It is still a great challenge to diagnose patients in an early stage of their disease. The delay between symptoms and diagnosis in SpA is still several years. As discussed above, it has been shown that in later stages of the disease, the treatment effect (even with bDMARDs) may be less impressive and chronic therapy is needed without possibility of drug withdrawal (leading to a high socioeconomic burden). The broad set-up of SPARTACUS across health institutes in Flanders will greatly facilitate the awareness and direct implementation of early arthritis strategies among physicians. Finally, results from SPARTACUS will provide evidence that will facilitate discussions with patients about treatment choices and ensure realistic treatment expectations and optimal health behaviour in patients with early pSpA.

6 End points

6.1 Primary end points

The primary endpoint of the study will be the comparison between the 2 treatment strategies at week 24 with regard to achievement of clinical remission (defined as complete absence of arthritis, dactylitis or enthesitis on clinical examination). At the week 24 timepoint, there are 3 possible scenario's (figure 3):

1. In patients that do not reach a state of clinical remission at week 24, blinded study medication will be interrupted and all patients will start open-label SC golimumab for an additional 36 weeks (up to max. week 60).
2. In patients that achieve sustained clinical remission at week 24, defined as absence of clinical arthritis, enthesitis and dactylitis at both week 12 and week 24, all study medication will be discontinued and prospective follow-up will be planned in SPARTACUS Phase B.
3. In patients that reach a state of clinical remission at week 24, but that did not yet reach this status at week 12, blinded study medication will be continued without any change in the treatment schedule for another 12 weeks.

6.2 Secondary end points

In addition to this, several secondary endpoints will be evaluated:

- Comparison between the “TNFi induction” group and the “csDMARD Step-up” group regarding:
 - o Achievement of “sustained clinical remission” at week 24 (and week 36 for the patients remaining on blinded study medication).
 - o Improvement from baseline to week 12 and 24 in individual clinical assessments (78-Tender Joint Count, 76-Swollen Joint Count, Dactylitis Count, SPARCC Enthesitis Score) and composite scores (ASDAS: Axial Spondyloarthritis Disease Activity Score).

- Improvement from baseline to week 12 and 24 in patient-reported outcomes (Patient global assessment of disease activity and pain, BASDAI, BASFI, ASAS Health Index).
- Improvement from baseline to week 12 and 24 in inflammatory parameters (ESR, CRP).
- Changes in concomitant NSAID intake (NSAID-index) and “escape” intra-articular glucocorticoid injections between baseline and week 24
- Difference in occurrence of (serious) adverse events (AEs) and AEs of specific interest between the 2 treatment strategies from baseline to week 24 (and week 36 for patients remaining on blinded study medication). Descriptive analysis of the number and type of adverse events between both strategies
- Percentage of patients achieving (sustained) clinical remission with open-label golimumab treatment after failure of the initial randomized, blinded treatment strategy.
- Exploration of difference in percentage of patients that reach (sustained) clinical remission according to symptom duration (<3 months versus ≥3 month and <12 months). The interaction between treatment group and symptom duration as a continuous predictor will also be analyzed to investigate the effect of symptom duration with regard to reaching the specified primary and secondary outcomes.
- For patients in SPARTACUS Phase B (drug-free remission period):
 - Exploration of the duration of drug-free remission.
 - Time to (documented) pSpA disease flare.
 - Time to restart of “standard-of-care” pSpA treatment.
 - Exploration of clinical parameters that could be predictive for reaching (sustained) clinical remission and/or flare.
- Correlation between the “Patient Acceptable Signs & Symptoms Improvement” (“PASSI”) and different clinical assessments, laboratory values and patient-reported outcomes (or combinations thereof).

7 Trial Design - The present study

7.1 Study design description

The SPARTACUS clinical trial is a prospective, randomized, active-comparator controlled, double-blind, double-dummy, phase III, national multicentric clinical trial which consists of 2 phases (duration phase A is up to 60 weeks, phase B up to 3 years):

SPARTACUS Phase A: “Remission-Induction Phase”:

[figure not shown]
(Baseline to (maximum) week 60: for a global overview see Addendum 2)

All patients (n=90) will be randomized (1:1) to either immediately receiving TNFi (golimumab) monotherapy (“TNFi Induction”-group) (n=45), or to the step-up regimen with csDMARDs (“csDMARD Step-up”-group) (n=45) (figure 1).

Synovial biopsies will be harvested during the screening period by ultrasound (US) guided biopsy for small joints (Metacarpophalangeal- (MCP) and proximal interphalangeal- joints (PIP) of the hands, metatarsophalangeal joints (MTP) of the feet) or certain large joints (elbow, wrist, knee, ankle). In case of multiple small joint involvement, a joint with a score of 2 or more on Grey Scale/Power Doppler US assessment will be chosen to sample.

The patients in the TNFi-induction group will receive golimumab at a standard dose of 50 mg subcutaneously (SC) every 4 weeks (with matching methotrexate (MTX)-placebo) (figure 1). In case of potential intolerance or toxicity to MTX-placebo (see paragraph 9.5.8 for known side effects of MTX) , the dose will be gradually tapered to a minimum of 7.5 mg per week. When there are no tolerability/toxicity issues, the weekly dose of MTX-placebo will be increased to 20 mg at week 4.

Figure 1: Baseline – Week 8

[figure not shown]

¹“Blinded MTX-Intolerance”-regimen can be initiated from week 4, but also at later study visits.

²In case of intolerance to MTX-Placebo 20 mg QW, the previous dose (15 mg) can be used.

The patients in the csDMARD-Step-up group (figure 1) will start with oral methotrexate (MTX) at a weekly dose of 15 mg for 4 weeks (with matching TNFi-placebo injections). In case of potential intolerance or toxicity to MTX (see paragraph 9.5.8 for known side effects of MTX), the dose will be gradually tapered to a minimum of 7.5 mg per week. When there are no tolerability/toxicity issues, the weekly dose of MTX will be increased to 20 mg at week 4. At week 12, a “Patient Acceptable Signs & Symptoms Improvement” (‘PASSI’) will be assessed by asking the question “*Taking into account both efficacy and side effects, did you experience over the past 12 weeks enough improvement in signs and symptoms of your’ arthritis-enthesitis-dactylitis to consider continuation of the same treatment schedule for the next 12 weeks?*” (see Addendum 3). If yes, all study medication will be kept stable until week 24; if no, oral sulphasalazine at a dose of 2 g per day will be started (escape medication) (figure 2).

Figure 2: Week 12 – Week 20

¹Continued “MTX-Intolerance” after tapering to 7.5 mg QW results in MTX-discontinuation
‘PASSI’: Patient Acceptable Signs & Symptoms Improvement

[figure not shown]
The need for concomitant intake of NSAIDs will be recorded (by calculating the NSAID-index); in case of persistent severe arthritis, a maximum of 2 intra-articular corticosteroid injections will be allowed (starting at week 12 after the clinical evaluations, but before the week 20 assessment). Both NSAID-index and number of corticosteroid injections will be considered as surrogate (in)efficacy markers. From week 20, all concomitant medication (see section 9) should be kept stable until the assessment of the primary endpoint at week 24.

The primary endpoint of the study will be the comparison between the 2 treatment strategies at week 24 with regard to achievement of clinical remission (defined as complete absence of arthritis, dactylitis or enthesitis on clinical examination). At the week 24 timepoint, there are 3 possible scenario’s (figure 3):

1. In patients that do not reach a state of clinical remission at week 24, blinded study medication will be interrupted and all patients will start open-label SC golimumab for an additional 36 weeks (up to max. week 60).

2. In patients that achieve sustained clinical remission at week 24, defined as absence of clinical arthritis, enthesitis and dactylitis at both week 12 and week 24, all study medication will be discontinued and prospective follow-up will be planned in SPARTACUS Phase B.
3. In patients that reach a state of clinical remission at week 24, but that did not yet reach this status at week 12, blinded study medication will be continued without any change in the treatment schedule for another 12 weeks.

[figure not shown]
Figure 3: Week 24 (Primary Endpoint)

At week 36 (figure 4), patients that have continued the blinded study medication, will be re-assessed regarding sustained clinical remission (at week 24 and 36): if yes, all study medication will again be discontinued and prospective follow-up will be planned in SPARTACUS Phase B. If no, these patients will start open-label SC golimumab for an additional 24 weeks (up to max. week 60).

If patients were in the “open-label golimumab treatment arm”, effectiveness of the treatment will be assessed by using the “PASSI”-question. Inadequate responders will be discontinued from the study and will be treated with standard-of-care medication at the discretion of their treating rheumatologist, whereas patients with an acceptable improvement in signs and symptoms will continue with the same (open-label) medication schedule.

[figure not shown]
Figure 4: Week 36

At week 48 (figure 5), all patients still remaining in SPARTACUS Phase A will have been treated with open-label golimumab (for a minimum of 12 weeks, but potentially up to 48 weeks). In patients reaching at this timepoint sustained clinical remission (at week 36 and 48), golimumab will be discontinued and prospective follow-up will be planned in SPARTACUS Phase B. For the other patients there are 3 possible scenarios:

[figure not shown]
1. Patients reaching clinical remission for the first time at week 48 will continue without any change in the treatment schedule for another 12 weeks.
2. Patients with an inadequate response (based on the "PASSI"-question), will be discontinued from the study and will be treated with standard-of-care medication at the discretion of their treating rheumatologist.
3. Patient with an acceptable improvement (but no clinical remission) will continue open-label golimumab treatment for an additional 12 weeks, but in these patients open-label methotrexate will be associated (unless contra-indicated) to fulfil Belgian reimbursement criteria for TNFi.

Figure 5: Week 48

At week 60 (final study visit of SPARTACUS Phase A) (figure 6), patients reaching sustained clinical remission (at week 48 and 60), will roll-over into SPARTACUS Phase B. All other patients will be discontinued and will be treated with standard-of-care medication (including TNFi, if in accordance with Belgian reimbursement criteria).

Figure 6: Week 60

SPARTACUS Phase B: “Drug-Free Remission Phase”: cessation of therapy and exploration of drug-free remission in patients that achieve sustained clinical remission while on therapy in phase A:

(Duration: max. 3 years)

After reaching ‘sustained clinical remission’, as defined above, all medication will be discontinued (possible timepoints for entering phase B would be week 24, 36, 48 and 60 of

phase A); the last study visit of Phase A will become visit 1 in Phase B. In this prospective study, all patients will be systematically followed and data about disease activity will be collected at predefined timepoints (every 12 weeks in the first year; thereafter every 24 weeks). This will allow us to explore the possibility of maintaining drug-free remission. If a flare occurs within 144 weeks after medication withdrawal, standard-of-care treatment will be started at the discretion of the treating rheumatologist; at that time, phase B will end. Patients who are still in drug-free remission and reach the Phase B final study visit at week 144 will be prospectively followed in the Be-GIANT cohort allowing further long-term follow-up.

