 - “Health Economic Evaluation”: EuroQoL 5 dimensions, co-morbidity Index (SCQ) and healthcare utilization and productivity (in the past 3 months)
 - Patient Acceptable Signs & Symptoms Improvement (“PASSI”) question (see Addendum 3).
- Targeted physical examination.
- Vital signs (blood pressure, heart frequency).
- Weight.
- Smoking/alcohol status
- Rheumatological examination (see Addendum 5):
 - 78-Tender and 76-swollen joint count.
 - Dactylitis assessment.
 - Enthesitis assessment (SPARCC Enthesitis Index).
 - Bath Ankylosing Spondylitis Metrology Index (BASMI), including tragus-to-wall distance, lumbar flexion (Schöber index), lumbar lateroflexion, cervical rotation and intermalleolar distance; chest expansion.
 - Psoriasis skin evaluation (if applicable).
 - Physician global assessment of disease activity (0-10 numerical rating scale).
- Laboratory investigation:
 - Disease activity: ESR, CRP.
 - Safety: peripheral blood count, serum creatinine, uric acid, liver function tests (ALT, gamma-GT, Alkaline Phosphatase, LDH), Creatine Kinase.
- Trial continuation evaluation based on clinical remission (yes/no) at week 36 and potential sustained clinical remission (at week 24 and 36):
 - Blinded continuation group:
 - No clinical remission: stop blinded study medication; start open-label golimumab 50 mg SC every 4 weeks.
 - Sustained clinical remission: stop blinded study medication; roll-over into SPARTACUS Phase B – visit 1.

- Open-label golimumab group: additional decision based upon “PASSI”-question (yes/no)
 - Clinical remission: continuation of open-label golimumab 50 mg SC every 4 weeks.
 - No clinical remission and “PASSI”-yes: continuation of open-label golimumab 50 mg SC every 4 weeks.
 - No clinical remission and “PASSI”-no: study discontinuation, further (standard-of-care) treatment at the discretion of the treating rheumatologist.
- For patients continuing in SPARTACUS Phase A: dispensation of study drug:
 - Administration of Golimumab injection at study site.
 - Dispensation of Golimumab injections for week 40 and week 44 administration at home. Education regarding self-injection.

Phase A – Visits 11: WEEK 48 (+/- 1 week)

- Assessment of adverse events.
- Tuberculosis Questionnaire.
- Current medication (dose and duration).
- Study drug accountability.
- Patient reported outcomes (see Addendum 7):
 - Patient global assessment of disease activity (0-10 numerical rating scale).

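### At week 36, section 7.1 discontinues open-label golimumab patients on the PASSI answer, whereas section 11.4.1 keeps everyone in clinical remission; a patient in remission who answers no gets opposite instructions.

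*Protocol*

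**What the plan says.** Two sections of the Protocol tell sites what to do at week 36 with patients already on open-label golimumab.

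- **Section 7.1 (Study design description, week 36).** For these patients "effectiveness of the treatment will be assessed by using the “PASSI”-question". The consequence of a poor answer follows: "Inadequate responders will be discontinued from the study and will be treated with standard-of-care medication at the discretion of their treating rheumatologist". Those who report enough improvement stay on open-label golimumab. Clinical remission does not appear in this rule.
- **Section 11.4.1 (Phase A, Visit 10, week 36).** PASSI comes in as a further criterion beside remission status: "Open-label golimumab group: additional decision based upon “PASSI”-question (yes/no". The first branch carries no PASSI condition: "Clinical remission: continuation of open-label golimumab 50 mg SC every 4 weeks". The only branch that leaves the study needs both conditions: "No clinical remission and “PASSI”-no: study discontinuation". Patients not in remission who answer yes continue.

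The PASSI question opens "Taking into account both efficacy and side effects" and asks whether the patient would consider continuing the same schedule. Clinical remission (section 6.1) is the absence of arthritis, dactylitis and enthesitis on examination.

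The result feeds a secondary endpoint in section 6.2: "Percentage of patients achieving (sustained) clinical remission with open-label golimumab treatment after failure of the initial randomized, blinded treatment strategy".

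**The concern.** PASSI is a patient's overall judgement that includes tolerability, while remission is an examination finding. A patient can have a clean examination and still answer no because of side effects. At week 36 section 7.1 sends that patient out of the study and section 11.4.1 keeps the patient on golimumab. The Protocol does not say which section prevails, so sites could handle identical patients differently.

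Patients who start open-label golimumab at week 24 are, by definition, not in remission then. They can reach sustained remission only through weeks 36 and 48 or through weeks 48 and 60. Those in remission at week 36 make up the whole of the first route. Removing one of them at week 36 forecloses the week-48 confirmation and hence entry to Phase B, where drug-free remission is studied.

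**Working it through.** **Step 1: the two rules compared (open-label patients, week 36).**

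| Clinical remission | PASSI | Section 7.1 | Section 11.4.1 | Agree? |
|---|---|---|---|---|
| Yes | Yes | Continue | Continue | Yes |
| No | Yes | Continue | Continue | Yes |
| No | No | Discontinue | Discontinue | Yes |
| Yes | No | Discontinue | Continue | **No** |

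The conflict is confined to the last row.

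**Step 2: which rule was intended.** At week 48, section 7.1 again ties inadequate response to PASSI. There, however, it first sends patients in sustained remission to Phase B and gives first-time remission its own scenario. It also counts remission at weeks 36 and 48 as sustained, which presupposes that patients in remission at week 36 stay on treatment. The week-36 open-label text has no remission branch. The likeliest reading is that 11.4.1 states the intended rule and 7.1 omits the exception.

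**Step 3: how many patients.** The Protocol gives no figure for this cell, so the size has to be built up.

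Inputs from the Protocol: 45 patients per arm (section 7.1) and planned remission of 20% versus 50% at week 24 (section 13.1).

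Inputs that are assumptions, with no basis in the Protocol:
- in remission at week 36 among open-label starters: 30% to 50%
- PASSI no among those in remission: 3% to 10%
- would have stayed on golimumab if allowed: 50% to 100%
- still in remission at week 48 if they stayed: 50% to 80%

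Open-label starters at week 24 = 45 × (1 − 0.20) + 45 × (1 − 0.50) = 36 + 22.5 = 58.5. This ignores dropout before week 24.

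Conflicting cell = starters × remission at week 36 × PASSI no:
- low: 58.5 × 0.30 × 0.03 = 0.53
- high: 58.5 × 0.50 × 0.10 = 2.93

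Sustained remissions and Phase B entries lost under 7.1 = cell × stay on treatment × remission held:
- low: 0.53 × 0.50 × 0.50 = 0.13
- high: 2.93 × 1.00 × 0.80 = 2.34

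As a share of starters: 0.13 / 58.5 = 0.2% and 2.34 / 58.5 = 4.0%.

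**Step 4: what is not touched.** Remission at week 36 is assessed at the visit where the decision is taken, so it is recorded under either rule. The primary endpoint is read at week 24, before the rule applies.

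**The case against.** The best defence is that section 7.1 is a shorter form of section 11.4.1. It does not say that PASSI overrides remission, and a patient with no arthritis, enthesitis or dactylitis is hard to call an inadequate responder. The visit-level text in 11.4.1 is complete, the flowchart schedules both PASSI and remission status at week 36, and Figure 4, which cannot be seen here, may draw the 11.4.1 rule. In addition, a patient in remission who answers no is probably troubled by side effects, and section 8.3.1 already lets such a patient, or the investigator, stop treatment. Some would therefore leave golimumab under either rule. All rates after week 24 are assumed, and the upper bound sets every one at its maximum together.

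Part of this stands. The intended rule can be inferred, the effect is small, and some affected patients would stop anyway, which the 50% to 100% range for staying on treatment allows for.

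The shorthand reading does not stand. Section 7.1 makes PASSI the stated measure of effectiveness at week 36, links inadequate response to PASSI explicitly at week 48, and at week 36 gives open-label patients no remission branch. Whatever Figure 4 shows, it cannot reconcile two written rules that differ. Section 8.3.1 also lets a patient stop treatment and remain in the trial, whereas the 7.1 rule ends study participation.

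**Conclusion.** The concern holds. The two week-36 rules contradict each other in exactly one cell, remission with PASSI no, and section 7.1 is the one that appears wrong. The conclusion about the text rests on the wording alone and needs no assumption.

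The size is small: about 0.5 to 2.9 patients in the cell and 0.1 to 2.3 lost sustained remissions and Phase B entries, or 0.2 to 4.0 percentage points of the 58.5 expected open-label starters. Those ranges depend on the assumed rates after week 24. The effect is limited to the sustained component of the open-label secondary endpoint and to Phase B entry. It should be corrected because it decides whether a patient in remission stays in the trial and because the correction is nearly free.

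**What to change.** Reword the week-36 sentence in section 7.1 to match section 11.4.1: open-label patients in clinical remission continue golimumab whatever they answer to PASSI, and only patients who are not in clinical remission and answer no are discontinued. Check that Figure 4 and Addendum 2 draw the same rule.

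For clarity only, add the condition of no clinical remission to the second week-48 scenario in 7.1. That text already fits 11.4.1 when the scenarios are read as alternatives.

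The cost is one clause and a check of one figure and one addendum. PASSI and remission status are already collected at week 36, and section 8.3.1 already requires withdrawal reasons to be recorded, so no new eCRF field is needed. Sample size and the primary analysis do not change.
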